2.10 Interim Analysis

No interim analysis is planned.

3 STUDY POPULATION

3.1 Definition of Subject Populations

All subjects who return to the clinic on Day 1 (i.e., study baseline) and have all required baseline (before injection of study medication) assessments/procedures completed will be considered study participants. Study populations are defined in the following sections to assess the safety and effectiveness of MYOBLOC.

Safety Population

The safety population is defined as all subjects who are injected with at least one dose of study medication. The safety population will be utilized for safety analyses. The safety population will be identified and finalized before database is locked.

Intention-to-treat Population

The intention-to-treat (ITT) population is defined as all subjects who are injected with study medication and have at least 1 post-baseline measurement recorded in the eCRF for both USFR and CGI-C. The ITT population will be used as the primary population for effectiveness analyses. The treatment group identification of a subject in the ITT population will follow those of the safety population.

3.2 Screening and Enrollment

An enrollment summary including the number of subjects enrolled (i.e., study participants), treated (i.e., safety population), efficacy evaluable (i.e., ITT population), and completed the study will be presented by site. Study participants include all individuals who have all required baseline (before injection of study medication) assessments/procedures completed at Day 1 visit. The number of subjects who received treatment doses will be summarized by session for safety population and for ITT population.

3.3 Population Demography

For the safety and ITT populations, descriptive summaries of demography will be presented.

Demography includes age in years (continuous and categorical 18 to 49, 50 to 64, 65 to 74, and 75+), sex, race, ethnicity, weight, and height. Demography will also be listed for all subjects enrolled.

3.4 Disease Diagnosis and Prior Therapy

For the safety population, descriptive summaries will be presented for disease diagnosis and use of prior therapy and for severity of troublesome sialorrhea at baseline. The protocol indicated summarizing severity of troublesome sialorrhea at baseline. These were summarized using disease severity at baseline as measured by USFR, DFSS-I, DFSS-S, CGI-C, PGI-S and DIS.

Disease diagnosis, USFR, DFSS-I, DFSS-S, CGI-S, PGI-S, and DIS score at baseline (i.e., Day 1), and use of prior therapy will be listed for all subjects enrolled.

The protocol indicated summarizing Disease Diagnosis and Prior Therapy, Medical History and Disposition for the safety and ITT populations, however since the difference between these two populations was only one subject, these were only summarized for the safety population.

3.5 Medical History

Medical history will be listed for the safety population.

3.6 Disposition of Study Participants

Subject disposition including completion and discontinuation along with CRF-based termination reason will be summarized for all enrolled subjects.) Subjects' early termination details will be listed for all subjects enrolled.

Subjects' treatment sequence and dose, and treatment date and time will be listed for all subjects treated.

3.7 Protocol Deviations and Violations

A summary of protocol deviation and violations will be provided. Subjects who are treated in the study, but not included in the ITT population will be listed.

4 EFFICACY EVALUATION

4.1 Datasets Analyzed

The ITT population is defined as the population for effectiveness analysis.

4.2 Treatment Compliance

For this study, the overall compliance rate will be summarized by demographic parameters for the safety population. For a treatment session, the compliance rate, expressed as percent, is calculated by dividing the number of drug injections into the 4 locations of the submandibular and parotid glands by the total number of 4 injections that should have been given during a treatment session multiplied by 100. For a subject, the overall compliance rate is defined as the average of compliance rates for all treatment sessions.

4.3 Baseline Measures

Descriptive statistics of the USFR, DFSS-I, DFSS-S, CGI-S, PGI-S, and DIS at baseline (or pre-injection) will be summarized within their corresponding tables indicated in the sections below.

4.4 Efficacy Results and Tabulations

Descriptive and inferential statistics of USFR (g/minute) and changes from pre-injection at Day 1 to Weeks 4, 8 and 13, for Treatment Session 1 and from each subsequent pre-injection at Weeks 13, 26 and 39 (Treatment Session 2, 3 and 4) to 4 and 13 weeks following it respectively, will be presented for the ITT population.

Descriptive and inferential statistics of DFSS-I and changes from pre-injection at Day 1 to Weeks 4, 8, and 13, for Treatment Session 1 and from each subsequent pre-injection at Weeks 13, 26 and 39 (Treatment Session 2, 3 and 4) to 4 and 13 weeks following it, respectively, will be presented for the ITT population.

Descriptive and inferential statistics of DFSS-S and changes from pre-injection at Day 1 to Weeks 4, 8, and 13, for Treatment Session 1 and from each subsequent pre-injection at Weeks 13, 26 and 39 (Treatment Session 2, 3 and 4) to 4 and 13 weeks following it, respectively, will be presented for the ITT population.

Descriptive and inferential statistics of CGI-S and changes from pre-injection at Day 1 to Weeks 4, 8, and 13, for Treatment Session 1 and from each subsequent pre-injection at Weeks 13, 26 and 39 (Treatment Session 2, 3 and 4) to 4 and 13 weeks following it, respectively, will be presented for the ITT population.

Descriptive and inferential statistics of CGI-C at pre-injection (except for Day 1), and at Weeks 4, 8, and 13 for Treatment Session 1 and from each subsequent pre-injection at Weeks 13, 26 and 39 (Treatment Session 2, 3 and 4) to 4 and 13 weeks following it, respectively, will be presented for the ITT population.

Descriptive and inferential statistics of the proportion of the CGI-C treatment responders with much improved or better at pre-injection (except for Day 1) and at Week 4, 8, 13 weeks post injection for Treatment Session 1 and from each subsequent pre-injection at Weeks 13, 26 and 39 (Treatment Session 2, 3 and 4) to 4 and 13 weeks following it, respectively, will be presented for the ITT population.

Descriptive and inferential statistics of PGI-S and changes from pre-injection at Day 1 to Weeks 4, 8, and 13, for Treatment Session 1 and from each subsequent pre-injection at Weeks 13, 26 and 39 (Treatment Session 2, 3 and 4) to 4 and 13 weeks following it, respectively, will be presented for the ITT population.

Descriptive and inferential statistics of PGI-C at pre-injection (except for Day 1), and at Weeks 4, 8, and 13 for Treatment Session 1 and from each subsequent pre-injection at Weeks 13, 26 and 39 (Treatment Session 2, 3 and 4) to 4 and 13 weeks following it, respectively, will be presented for the ITT population.

Descriptive and inferential statistics of the proportion of the PGI-C treatment responders with much improved or better at pre-injection (except for Day 1) and at Week 4, 8, 13 weeks post injection for Treatment Session 1 and from each subsequent pre-injection at Weeks 13, 26 and 39 (Treatment Session 2, 3 and 4) to 4 and 13 weeks following it, respectively, will be presented for the ITT population.

Descriptive and inferential statistics of DIS and changes from pre-injection at Day 1 to Weeks 4, 8, and 13 for Treatment Session 1 and from each subsequent pre-injection at Weeks 13, 26 and 39 (Treatment Session 2, 3 and 4) to 4 and 13 weeks following it, respectively, will be presented for the ITT population.

5 SAFETY EVALUATION

For safety evaluation, the safety population as defined in Section 3.1 will be utilized to conduct safety analyses.

5.1 Extent of Drug Exposure

Number of MYOBLOC dose injections will be tabulated as continuous variable as well as categorical variable, using the categories of 1 injection, 2 injections, 3 injections, and 4 injections.

Average duration and total duration of treatment sessions, following dose injection, will be also tabulated.

Individual subjects' number of treatment sessions and duration of treatment session will be listed for the safety population .

5.2 Early Termination

Early termination from study will be categorically summarized by subject population. Subjects' study termination details will be listed.

5.3 Adverse Events

An overall summary of AEs reported in this study will be provided for each treatment session.

Incidences of subjects reporting treatment-emergent AEs will be reported for each treatment session.

The severity of the treatment-emergent AEs will be summarized for each treatment session.

The relationship to study drug of the treatment-emergent AEs will be summarized for each treatment session.

Treatment-emergent AEs associated with early terminations will be summarized for each treatment session.

Serious AEs (including death) will be summarized for each treatment session.

Narratives will be presented for all deaths, non-fatal serious adverse events and subjects withdrawn due to adverse events.

Details of all TEAEs will be listed for each subject of the safety population in listings. Details of AEs associated with early terminations will be listed for individual subject. SAEs including deaths will be listed for each event.

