2.9.2 Safety analysis

Safety measures include adverse events, adverse events of special interest (AESI), dental adverse events (DAE), adverse events associated with distant spread of toxin effect, vital signs and weight, physical exam, neurological exam, dental exam, oral exam, and clinical laboratory tests, as well as lung functioning test for ALS subjects. Adverse events will be coded using the Medical Dictionary for Regulatory Activities (MedDRA) adverse event dictionary.

Like for effectiveness analyses, the baseline for safety analysis includes the pre-injection visits of Day 1, and Weeks 13, 26, and 39, respectively, for each of the treatment sessions 1 through 4.

Drug Exposure

Frequency of drug exposure will be calculated based on the number of injections of study drug administered. Duration of drug exposure will be calculated for each subject for the average duration of individual treatment sessions and total duration of treatment sessions, with the former being the average of the durations of individual treatment sessions the subject has received and the latter being the sum of the durations of individual treatment sessions the subject has received. Duration of drug exposure will be summarized for the safety population as defined in Section 3.1.

Early Termination

Subjects' study disposition will be summarized. A listing will be provided for all early terminations. This listing will include a subject's demographic variables, primary diagnosis, number of injections administered, and the primary reason for early termination.

Adverse Events, AESI, and DAE

All of adverse events will be coded for preferred terminologies using MedDRA. An AE that occurs on the 1st injection date or later will be defined as a TEAE. An AE with start date missing and no valid stop date or stop date being after the first injection date will be considered as a TEAE. TEAEs will be further separated by treatment session.

TEAEs, AESIs, DAEs, and adverse events associated with distant spread of toxin effect will be analyzed by session. Frequency of these types of adverse events will be calculated for each body system (or system organ class, SOC), by preferred term, for number of subjects and proportion reporting the event. The severity of adverse events and the relationship to study medication will be summarized for each body system and preferred term.

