Withdrawals due to adverse events will be summarized for each body system and preferred term. Serious adverse events (SAEs) (including deaths) will be listed for individual events.

Narratives will be provided for all deaths, non-fatal serious adverse events, and subjects withdrawn due to adverse events.

Vital Signs and Weight

Vital signs and weight will be summarized descriptively by treatment session at pre-injection (i.e., Day 1 and Weeks 13, 26, and 39) and at each post-injection time point of 4 weeks post-injection (i.e., Weeks 4, 17, 30, and 43), 8 weeks post-injection (i.e., Week 8 first treatment session only), and 13 weeks post-injection (i.e., Weeks 13, 26, 39, and 52). The change scores in vital signs and weight from baseline at 4 weeks, 8 weeks (first treatment session only), and 13 weeks post-injection will be summarized descriptively.

Neurologic Exam

Abnormal findings of neurological exam data will be listed, respectively, for individual subjects.

Lung Functioning Test

Findings of forced vital capacity (FVC) data will be listed, respectively, for individual subjects.

Physical Examination

A complete Physical Examination was performed at Screening, Week 4, Week 13, Week 26, Week 39, Week 52, and Early Discontinuation. A brief Physical Examination was performed at Day 1, Week 8, Week 17, Week 30, and Week 43 when body weight, height and body mass index (BMI) were recorded. If any of the Physical Examination findings were abnormal and clinically significant prior to treatment, the event was recorded as medical history, while if occurred after treatment the event was recorded as a TEAE.

Suicidality Assessment

For each treatment session, each of the three C-SSRS subscales (suicidal ideation, suicidal behavior, and intensity of suicidal ideation) will be summarized descriptively for continuous variable at each pre-injection visit (i.e., Day 1 and Weeks 13, 26, and 39) and at each post-injection time point of 4 weeks post-injection (i.e., Weeks 4, 17, 30, and 43), 8 weeks post-injection (i.e., Week 8, first treatment session only), and 13 weeks post-injection (i.e., Weeks 13, 26, 39, and 52). The change scores in C-SSRS subscales from pre-injection at 4 weeks, 8 weeks (first treatment session only), and 13 weeks post-injection will be summarized descriptively.

Dental Examination and Oral Examination

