5.4 Adverse Events of Special Interest (AESI)

Analyses of AESI will include aspiration, aspiration pneumonia, choking, and dysphagia. Incidences of subjects reporting AESI will be reported for each treatment session. Details of AESIs will be listed for individual subjects will be listed.

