5.5 Adverse Events Associated with Dental Disease

Incidences of subjects reporting adverse events associated with dental disease, per sponsor-provided list, will be reported for each treatment session.

Table B – Listing of Dental Disease Terms used for Analysis

Term		
Angular cheilitis	Breath odour	Bruxism
Candida infection	Chapped lips	Dental caries
Dental leakage	Dental necrosis	Device failure
Gingival bleeding	Gingivitis	Glossitis
Glossodynia	Haemoptysis	Lip swelling
Mouth cyst	Mouth swelling	Mucosal inflammation
Mucosal ulceration	Oral candidiasis	Oral discomfort
Oral pain	Periodontitis	Pulpitis dental
Sensitivity of teeth	Stomatitis	Swollen tongue
Tongue coated	Tongue discolouration	Tongue dry
Tooth abscess	Tooth fracture	Tooth infection
Tooth injury	Tooth loss	Toothache

Details of AEs associated with dental disease will be listed for each subject.

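### The SAP text reports adverse-event incidence by treatment session and commits to no count of subjects affected over the whole study

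*SAP*

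**What the plan says.** SAP 1.1 sets the primary objective as long-term safety and tolerability of treatment every 13 weeks for up to a year.

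SAP 2.9.2 counts as treatment-emergent any event on or after the first injection date and then says "TEAEs will be further separated by treatment session". It continues: "TEAEs, AESIs, DAEs, and adverse events associated with distant spread of toxin effect will be analyzed by session". Its sentences on severity, relationship to study drug and withdrawals name no session. For serious events it says only "Serious adverse events (SAEs) (including deaths) will be listed for individual events".

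SAP 5.3 applies the session cut throughout. It says "Incidences of subjects reporting treatment-emergent AEs will be reported for each treatment session", and likewise "An overall summary of AEs reported in this study will be provided for each treatment session" and "Serious AEs (including death) will be summarized for each treatment session". Severity, relationship and events tied to early termination are also given by session.

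SAP 5.4 says "Incidences of subjects reporting AESI will be reported for each treatment session". SAP 5.5 says "Incidences of subjects reporting adverse events associated with dental disease, per sponsor-provided list, will be reported for each treatment session". SAP 5.6 does the same for distant spread of toxin effect. Protocol 17.7 likewise gives treatment-emergent frequencies by session.

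**The concern.** A reader of a one-year safety study will first ask how many treated subjects had a given event at any time. The text answers a different question, four times over: how many had it in Session 1, in Session 2, and so on.

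The session figures cannot in general be turned into the whole-study figure, for two reasons. A subject who reports dysphagia in two sessions appears in both tables. The group at risk also changes. Only Sessions 1 and 2 are required (SAP 2.3, Table B footnote), and ALS subjects may enter with availability for only 6 months (Protocol 11.1.1), so the later-session groups can differ in disease mix as well as in size.

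At stake is whether the plan commits in advance to the most direct summary of its primary objective, or leaves it to be worked out from listings afterwards.

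**Working it through.** **Plan's own figure.** There is none to reproduce. SAP 2.5 says that no sample size estimation was done; it names 187 subjects, and that N is used below.

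**Inputs.** N = 187 (SAP 2.5). Up to 4 sessions, of which 2 are required (SAP 2.3 and 5.1). The numbers affected per session and the fraction leaving are assumptions, not trial data.

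**Formula.** Let x₁, …, x_k be the numbers of subjects with the event in sessions 1 to k. The number with at least one event over the study, U, satisfies

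max(x₁, …, x_k) ≤ U ≤ min(N, x₁ + … + x_k).

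The lower end means that the same subjects are affected every time; the upper end means that no subject is affected twice.

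**Results.**

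| Assumed affected per session | Fewest distinct subjects | Most distinct subjects |
|---|---|---|
| 9, 9 | 9 (9/187 = 4.8%) | 18 (18/187 = 9.6%) |
| 9, 9, 9, 9 | 9 (4.8%) | 36 (36/187 = 19.3%) |
| 19, 19 | 19 (19/187 = 10.2%) | 38 (38/187 = 20.3%) |
| 19, 19, 19, 19 | 19 (10.2%) | 76 (76/187 = 40.6%) |
| 19, 19, 11, 11 | 19 (10.2%) | 60 (60/187 = 32.1%) |

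The last row assumes that 40% leave after Session 2: 0.6 × 187 = 112 remain, and about 10% of them is 11. The session percentages then stay almost flat (19/187 = 10.2%, 11/112 = 9.8%), while the whole-study proportion could be anywhere from 10.2% to 32.1%.

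As a point inside the range: with 5% per session, nobody leaving and independent sessions, the whole-study proportion is 1 − 0.95⁴ = 18.5%. Independence is a further assumption; if the same subjects tend to be affected again, the figure moves towards the lower end.

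**Events that occur once.** For death, x₁ + … + x_k equals U, because no subject is counted twice. Withdrawal due to an adverse event is nearly the same, since Protocol 12.3 bars re-entry. The exception is a withdrawal attributed to several events that began in different sessions, which Protocol 16.2.2.3 allows.

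**The case against.** The strongest objection is that the absence cannot be fully established. The SAP's contents list table shells in Section 7, and those pages were not available for this review. An all-sessions column is just what a shell would show. This stands: the point concerns the text, and a reader who infers that the whole-study count will go unreported goes further than the documents allow.

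Some wording also leans towards a pooled analysis. The treatment-emergent definition covers the whole study before the events are separated by session, and several sentences in 2.9.2 carry no session qualifier. Protocol 17.7 adds a subject incidence that omits events attributed to the underlying disease, again without session wording. None of these names a whole-study count of all treatment-emergent events, and 5.3 places severity, relationship and early-termination events back within session. The single dose column in SAP 2.9 pools doses, not sessions.

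The data are preserved. Treatment-emergent, special-interest, dental and distant-spread events are listed by subject, serious events are listed individually, and deaths, serious events and withdrawals due to adverse events get narratives. The count can therefore be derived. This stands too, and it limits the point to one about commitment.

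Three stronger readings are tempting, and the documents do not support them:

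- *That the SAP departs from the protocol.* Protocol 17.7 also summarizes treatment-emergent frequencies by session.
- *That no session count can be added.* Deaths, and largely withdrawals due to adverse events, can be.
- *That change in weight and vital signs over the year is lost because baseline resets each session.* Each session's 13-week visit is also the next session's pre-injection visit (SAP 2.3, Table A note d and Table B note c). For a subject with all visits, (Wk 13 − Day 1) + (Wk 26 − Wk 13) + (Wk 39 − Wk 26) + (Wk 52 − Wk 39) = Wk 52 − Day 1. If nobody's weight changed, all four planned mean changes would be zero, whoever left. A direct Day 1 to Week 52 row would add only a mean and SD in a single cohort.

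**Conclusion.** The point holds for the SAP text as available. Adverse-event incidence is assigned to treatment sessions, including the summary described as overall, and no sentence commits to a count of distinct subjects over the study.

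For recurring events, k sessions with equal counts leave the whole-study count uncertain by up to a factor of k: twofold over two sessions and fourfold over four. The percentages shown depend on assumed session counts and an assumed drop-out; they are bounds and do not predict where the trial lies.

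The summaries are descriptive, and no test or error rate is affected. The change is worth making because it bears on the primary objective. Confidence is moderate, because the shells may already contain the column.

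**What to change.** In SAP 2.9.2 and 5.3 to 5.6, add an all-sessions column to the tables of treatment-emergent, serious, special-interest, dental and distant-spread events. Define it as the number and percentage of subjects with at least one such event from first injection to end of study, with the full safety population as denominator. Keep the session columns beside it. If the shells already hold the column, say so in the text.

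Two additions are optional:

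- A row for within-subject change in weight and vital signs from Day 1 to Week 52 (n, mean, SD).
- An exposure-adjusted rate, since planned participation runs from 26 to 52 weeks (Protocol 10). If given, use first events over time to first event, or all events over total follow-up; do not divide subjects with an event by total exposure.

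The cost is SAP wording and a few table columns, or one sentence if the shells already comply. No new data are needed.

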5.4 Adverse Events of Special Interest (AESI)

Analyses of AESI will include aspiration, aspiration pneumonia, choking, and dysphagia. Incidences of subjects reporting AESI will be reported for each treatment session. Details of AESIs will be listed for individual subjects will be listed.

